2.1 Rationale for the study design

In this study we aim to conduct a Phase I clinical trial to assess the safety and feasibility of *in vitro* expansion of thymus-derived Tregs derived from explanted thymic tissue during surgery (or at the time of having a pump assist device fitted) and infusing them into 9 paediatric cardiac transplant recipients as a potential treatment to prevent CAV.

The first patient in Cohort 1 will receive TR006 and we will confirm the safety of the infused cell product following the treatment before infusing the next patient with at least a 4-week gap. Safety data that spans first four weeks post-dose will be made available from the database to the Data Monitoring Committee (DMC) who will assess this information to determine if the study can proceed with further recruitment and treatment.

After safety is confirmed for the first patient, the second and third patients will receive the same dose of TR006. A safety review will be done after the third patient to decide the dose for the next

cohort (Cohort 2). The same process will be done for the next cohorts (Cohort 2 and Cohort 3). A 3+3 strategy is employed to allow for expansion of the lower dose cohort in the event of any DLT or to allow for the higher dose cohort to begin sooner if there are no DLTs experienced at the lower dose.

In vitro cellular assays of anti-donor alloreactivity before and after Treg infusion will provide surrogate indicators of potential efficacy in promoting immune tolerance to the transplant antigens. The proposed research will yield valuable data on the applicability and safety of thymic Tregs for adoptive cell therapy in paediatric heart transplant patients. Results from this study will determine the optimal dose of injected Tregs. This will give the opportunity to test our strategy in a Phase II clinical trial where a larger cohort of patients will be tested. In addition, this will provide the opportunity to involve new national and international transplant centres for creating a consortium aiming to evaluate the efficacy of Treg therapy in children receiving heart transplant.

2.2 Rationale for dose and regimen selection

As part of Cohort 1, 3 patients will be treated with the first low dose of 1-3 x 10⁶Tregs/kg. If well tolerated, a further 3 patients will be treated with the second higher dose of 5-10 x 10⁶Tregs/kg as part of Cohort 2. If a DLT is observed, this second cohort of 3 will continue to be treated with the low dose. An additional 3 patients will form Cohort 3 and will be enrolled at the highest tolerated dose to test the biological activity of the Tregs. Should enrolment at the high dose only begin from the third cohort i.e. from participant 7 and 1/3 DLT is observed at this dose, further funding will be sought to expand this cohort to 6 and therefore treat a total of 12 participants.

The 2 doses were selected to match what we estimate to be the Minimal Anticipated Biological Effect doses based on the ThRIL and ONE studies [10,11]. This will allow us better to capture the safety of the product and biological activity at the selected dose in a more robust manner and also to provide information on the immunological effects of the Treg product.

In our work leading up to this study, we developed a protocol appropriate for translation of expanded thymic Tregs in our GMP facility at Guy's Hospital [12]. We established that 3 different steps are necessary to obtain the Treg product from the thymus; i) Tissue homogenisation, ii) Treg isolation and iii) Treg expansion.

Thymocytes were obtained from discarded thymi combining enzymatic and non-enzymatic procedures. We processed 12 thymi from children aged between 1 month and 13 years undergoing heart surgery. The medium yield of thymocytes isolated from a paediatric thymus was 0.64×10^9 cells/gr of tissue (range 0.35 - 1.08). Thymocytes obtained during this initial phase have been used for Treg isolation. CD3+CD4+CD8-CD25+ T cells were isolated by depleting CD8+ cells using immunomagnetic beads (CD8 microbeads, Miltenyi Biotec) followed by CD25 enrichment (CD25 microbeads, Miltenyi Biotec). The medium final cell yield was 2.19×10^6 Tregs/gr (range 0.59 - 4.03), indicating that from a single thymus, more than 10^7 Tregs can be isolated. The final Treg product had a high cell purity as the percentage of CD3+CD4+CD8-CD25+CD127low was above 80% (range 72-90.8%).

Isolated Tregs were expanded polyclonally using anti-CD3/CD28 coated beads (1:1 bead:cell ratio, MACS GMP ExpAct Treg Kit, Miltenyi Biotec) for 36 days in the presence of rapamycin (100nM) and IL-2 (1000 IU/ml; Proleukin, Novartis). The mean Treg fold expansion obtained from 7 different donors was 1589, range 221-3500 a number compatible with the infusion of more than 10⁷ cells per kg (highest dose planned in this clinical trial).

The final product has been functionally and phenotypically tested and all the cells were CD4+CD25+CD127- and CD4+CD25+Foxp3+. In addition, we evaluated the expression of other markers essential for Treg homing and function. In detail, Tregs were all positive for CTLA4, CD62L, CXCR4 and Helios while homing receptors like CCR6, CCR7, CXCR3 and functional markers like CD39 were poorly expressed. We also evaluated the function of the final products showing the ability of expanded Tregs to suppress the proliferation of third-party effectors T cells (Teffs) in a dose-dependent manner. Stability was also evaluated by activating Tregs in the presence of two pro-inflammatory cocktails known to mediate Tregs conversion in detrimental T-helper 17 cells. However, no IL-17 producing cells were detected at the end of the culture. Altogether these data clearly demonstrate that Tregs obtained with this protocol are functional, stable and appropriate for their translation to the clinic.

3 Trial Objectives and Endpoints

3.1 Aim

We are aiming to inject thymic-derived polyclonally expanded Tregs as a potential treatment to prevent CAV in 9 children receiving heart transplant. The purpose of this Phase I trial is to assess the safety of thymus derived Tregs (TR006) in the treatment of paediatric heart transplant patients and assess the technical feasibility of generating Tregs from the thymus.

3.2 Objectives and endpoints

Objectives	Outcome Measures/Endpoints
Primary Objective: To determine safety and optimal tolerated dose of TR006 to prevent CAV in paediatric heart	Primary Endpoint: Occurrence and nature of Dose-Limiting Toxicities (DLTs) occurring within 4 weeks post-
transplant patients in a phase I study.	infusion of the expanded autologous thymus derived Treg product (ATIMP).
Secondary Objectives:	Secondary Endpoints:
1. To assess the feasibility of generating TR006 in the Good Manufacturing Practice facility.	Amount of TR006 manufactured per patient.
2. To investigate the clinical and immunological	Assessment of Immunological response:
responses to TR006 in paediatric heart	• Frequency of circulating leukocyte subsets.
transplant patients.	• Quantity of alloantigen-specific conventional T cells, Tregs and CD8+.
	 Presence of anti-HLA to evaluate tissue infiltrating cells.
	Assessment of clinical response:
	• Diagnosis of CAV as measured by coronary angiography within 24 months post-infusion of TR006.
	 Graft loss as measured by inclusion of patient on the re-transplant waiting list through rejection (acute or chronic) within
	24 months post-infusion of TR006.
	• Recipient mortality within 24 months post- infusion of TR006.
	 Acute graft rejection as measured by endomyocardial biopsy (EMB) within 24 months post-infusion of TR006.
	• Antibody-mediated rejection as measured by development of donor specific antibodies within 24 months post-infusion of TR006.

r	
	 Infection related rehospitalisation events within 24 months post-infusion of TR006.
	 (Cardiac function) Left ventricular ejection fraction as measured by echocardiography monthly for 12 months and at 24 months post-infusion of TR006.
	 (Renal function) Mean calculated GFR at 24months post-infusion of TR006.
	• Description of non-DLT adverse events and those occurring beyond week 4 and up to 24 months post-infusion of TR006.
	 Immunosuppressive doses at 12 and 24 months post-infusion of TR006.
3. To assess the feasibility of retaining participants for the duration of the study and completion of study visits and assessments	Number of study visits completed per participant.
	 Responses to items in questionnaires or surveys exploring the study and treatment experience of the participants and their parents/guardians.

4 Assessment and Management of Risk

This study is a Phase I, single-center clinical trial of treatment with autologous thymus-derived Tregs. The first patient in the Cohort 1 will receive the treatment and we will confirm the safety of the infused cell product following the treatment before infusing the next patient (with at least a 4-week gap). After safety is confirmed for the first patient, the second and third patients will receive the same dose of TR006. A safety review will be done after the third patient to decide the dose for the next cohort (Cohort 2). The same process will be done for the next cohorts (Cohort 2 and Cohort 3).

The first cohort (Cohort 1) of patients (n=3) will be treated with a low dose of $1-3 \times 10^6$ Tregs/Kg. Dose escalation to the higher dose (5-10 x 10^6 Tregs/Kg) will only occur if the lower dose is considered well tolerated. In the event a DLT is observed, this will result in expansion of the lower dose cohort.

Participants will be monitored closely for 6 hours during and immediately after TR006 infusion and then also overnight for admission after the TR006 infusion in case of acute toxicity and to facilitate ease of regular sample collection for safety monitoring.

Following discharge, participants and/or their parents/legal guardians will receive daily phone calls for the first two weeks post TR006 infusion (except on day 14 post-dose) to monitor for any adverse events. Participants will be reviewed in person at days 14 and 28 post Treg infusion for safety assessments including clinical blood tests, ECG and echocardiography and continued adverse event monitoring. Thereafter, participants will be reviewed in person at months 2, 3, 6, 9 and 12 post-dose, with a final safety follow-up visit at 24 months post Treg infusion to monitor for any delayed or chronic complications.

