- 2. The TR001 phase I/II study based at Oxford and King's College London (NCT02129881) comprised 15 patients who were enrolled into the trial; 2 patients were withdrawn due to failure to expand sufficient Tregs (n=2) and one due to bacterial contamination of the Treg product. Out of 12 remaining patients, there were no Serious Adverse Reactions (SARs) or episodes of graft rejection, and a lower incidence of opportunistic infections compared to the reference group. Participants received cell therapy alongside standard of care immunosuppression. Infused cell doses are shown in Table 1. In a new currently ongoing trial, TR001 is being administered to living-donor kidney transplant recipients as part of a single centre phase II trial The TWO Study. The overall aim of this study is to evaluate the efficacy of Tregs in renal transplantation [9].

Results of the King's College London and Oxford study were pooled and published as with the ONE study, with a detailed paper of the Treg trial to follow [10]. Analysis of the adverse event data showed no safety issues when compared to the reference group trial. Infection rates were lower in the trials of cell-based medicinal products but the rejection rate was found to be similar across all trials.

Another phase I study (NCT02088931) from University of California treated 3 renal transplant recipients with an absolute Treg cell dose each of 319, 321 and 364x10⁶ (equivalent to 4.5x10⁶/kg, 4.6x10⁶/kg and 5.2x10⁶/kg assuming a body weight of 70kg). There were no opportunistic infections or SAEs, no CMV or polyoma neuropathy, no rejection, or cases of donor specific antibodies at one-month post infusion [26].

Autoimmune disorders

Clinical trials using autologous expanded Tregs have been conducted in specific autoimmune disorders, namely type I diabetes, and systemic lupus erythematosus, summarised in **Table 1** below).

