8.5 Dosage modifications

If the required dose cannot be manufactured the patient may have to be dosed at a lower dose than the dose originally planned. In such a situation, the Data Monitoring Committee and Statisticians should be informed.

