8.12 Participant Withdrawal Criteria

Participants have the right to withdraw from the study at any time for any reason. The investigator also has the right to withdraw patients from the study in the event of inter-current illness, AEs, SAE's, SUSAR's, protocol violations, cure, administrative reasons or any other reasons deemed appropriate. It is understood by all concerned that an excessive rate of withdrawals can render the study un-interpretable; therefore, unnecessary withdrawal of patients should be avoided. Should a patient decide to withdraw from the study, all efforts will be made to report the reason for withdrawal as thoroughly as possible.

As the IMP in this trial is an advanced therapy with a single infusion, participants who wish to withdraw from trial after IMP has been administered, will be asked to confirm whether they are still willing to attend the safety follow up visits as per protocol for the duration of the trial. If participants are not willing to do this, consent will be sought for the trial team to access routine data collected from hospital/GP visits for the duration of the safety follow up period.

In situations where a patient has to be withdrawn or decides to withdraw from the study, an additional patient may be recruited and dosed if:

- They withdraw prior to the TR006 infusion.
- They withdraw during their 4-week follow-up period, and have not yet experienced a DLT.

If a patient withdraws from the trial a withdrawal form in the study database will be completed.

The DMC will review all patients, including any withdrawn patients, to determine if a primary outcome has occurred (DLT, no DLT or DLT not determined in the active period).

In the following situations, the withdrawn patient will have contributed to the primary outcome and no additional patient will be recruited:

- If they withdrew after they completed their 4-week follow-up safety period.
- If they experience a DLT during their 4-week follow-up safety period, which may or may not be the reason for withdrawal.

9 Assessment of Safety

Definitions

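### The endpoint for manufacturing feasibility is an amount of cells, which does not show whether a usable product at the planned dose was made

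*Protocol*

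**What the plan says.** Feasibility of manufacture stands beside safety in the purpose of the trial. Protocol section 3.1 sets out to "assess the technical feasibility of generating Tregs from the thymus", and secondary objective 1 in section 3.2 is "To assess the feasibility of generating TR006 in the Good Manufacturing Practice facility". The only endpoint listed against that objective is "Amount of TR006 manufactured per patient". No release condition, dose requirement or definition of success goes with it.

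Other sections bear on the point:

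- Section 4.2.3 makes the final product subject to release criteria held in the IMPD. The endpoint does not refer to them.
- Section 8.5 provides for short batches: "If the required dose cannot be manufactured the patient may have to be dosed at a lower dose than the dose originally planned". The DMC and the statisticians are to be told.
- Section 8.12 allows an additional patient to be recruited where the condition "They withdraw prior to the TR006 infusion" is met.
- Section 10.1 reports clinical and immunological responses descriptively, and every other secondary endpoint as a rate with a 95% confidence interval.
- Section 10.5 includes all eligible recruited participants in the analysis, and section 7.10 keeps data gathered before a withdrawal.

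**The concern.** The feasibility question is whether a child whose thymus is collected ends up with a product that can be released at the dose intended for that child. A count of cells answers a different question, namely how much was grown. The two can part company in three ways.

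1. **Release.** A contaminated batch may have expanded normally. Its amount then looks like a success although nothing can be given.
2. **Dose.** A batch below the planned dose appears as a smaller number, but nothing marks it as having missed its target.
3. **Scale.** Section 6.1 admits children from 0.5 to 16 years and the dose is per kg, so a mean or median of absolute amounts mixes batches with very different requirements.

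The stated summary does not fit either, because an amount has no rate until success is defined. The trial could therefore report a healthy average yield and leave the reader to work out how many children had a usable product.

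**Working it through.** **The figure from the earlier trial.** Section 1.4 describes a kidney-transplant Treg trial that "comprised 15 patients who were enrolled into the trial". It then reports that "2 patients were withdrawn due to failure to expand sufficient Tregs (n=2) and one due to bacterial contamination of the Treg product", and continues "Out of 12 remaining patients". The counts agree: 15 - 2 - 1 = 12. The loss is 3/15 = 20.0%, with an exact (Clopper-Pearson) 95% interval of 4.3% to 48.1%. The protocol does not print the percentage.

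**How likely the problem is to arise.** The protocol gives no failure rate for TR006, so the rate p is an assumption. If batches fail independently, the chance of at least one failure in n batches is 1 - (1 - p)^n. The planned size is 3 cohorts x 3 = 9, or 9 + 3 = 12 if expanded.

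| Assumed p | n = 9 | n = 12 |
|---|---|---|
| 5% | 37.0% | 46.0% |
| 10% | 61.3% | 71.8% |
| 20% | 86.6% | 93.1% |
| 30% | 96.0% | 98.6% |
| 40% | 99.0% | 99.8% |

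At n = 9 and p = 20%, for example, 1 - 0.8^9 = 0.866.

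**What one amount means at two weights.** The weights of 7 kg and 50 kg are assumed; the dose ranges are those of section 8.1.

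- The lower end of the high range is 5 x 10^6 x 7 = 3.5 x 10^7 cells at 7 kg, and 5 x 10^6 x 50 = 2.5 x 10^8 cells at 50 kg. The ratio is 50/7, about 7.
- The upper end of the high range at 7 kg is 10 x 10^6 x 7 = 7 x 10^7 cells. Given to a 50 kg child, that amount is 7 x 10^7 / 50 = 1.4 x 10^6 per kg, inside the low range and well below the high one.

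**What a proportion would look like.** At an assumed 20% failure rate, dosing 9 children needs about 9/0.8 = 11.25 collections, and dosing 12 needs 12/0.8 = 15. Exact 95% intervals for such results are:

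- 9/11 = 82% (48.2 to 97.7%)
- 9/12 = 75% (42.8 to 94.5%)
- 12/15 = 80% (51.9 to 95.7%)

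**The case against.** The other side has a good case on several points.

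- **No patients are hidden.** A reader might infer that replacement under section 8.12 lets the trial count only infused children and report 9 of 9. The documents do not support this. The endpoint is per patient, and sections 10.5 and 7.10 keep recruited and withdrawn children in. The per-protocol restriction in section 10.1 is attached to clinical and immunological responses. Replacement adds a child and does not remove one.
- **Most failures would leave a trace.** A failed or short expansion shows as a nil or low amount. Withdrawal reasons go into the eCRF, and the DMC and statisticians hear of reduced doses.
- **A child who is never infused is not, for that reason, a manufacturing failure.** The objective concerns production in the GMP facility.
- **The 20% is not a forecast.** It comes from kidney-transplant recipients, and section 1.1 says that published Treg trials used blood-derived cells. None of the three losses was a child treated at a reduced dose.
- **Some of the remedy is SAP detail.** Exact intervals, scoring an absent product as zero and listing reasons could all be settled in the SAP.
- **A dose-based criterion needs a dose.** Thymus may be collected up to a year before transplant, while the dose level follows cohort safety reviews.

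The first five points stand and narrow the finding. They do not remove it. The endpoint variable is fixed in the protocol, it carries no link to release or to the required dose, and it does not match its own stated summary. The last point is met in part by section 8.6, which has the product formulated to a concentration for the patient dose, so a planned dose exists once a batch reaches formulation.

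**Conclusion.** The point holds as a weakness of the endpoint variable. The amount manufactured does not separate usable from unusable product. The clearest gap is a batch that expands but fails release. The missing dose criterion, the missing per-kg scale and the mismatch with section 10.1 add to it.

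Its size cannot be fixed from the protocol. Over an assumed failure rate of 5 to 40%, with independent batches, at least one failure among 9 has a chance of 37 to 99%, so the case may well arise. Those figures cover manufacturing failures of any kind; release failures alone would be fewer. The 3 of 15 shows that both failed expansion and contamination have occurred with a related product, and supports no more than that.

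This is a descriptive secondary endpoint and the primary safety endpoint is untouched. It is an inexpensive improvement and not a defect that threatens the trial.

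**What to change.** Replace the endpoint for secondary objective 1 with the proportion of participants with thymus collected for manufacture whose batch passed release and met the per-kg dose range planned when the product was formulated, using the weight used for formulation. Report it with an exact 95% confidence interval.

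- Put every participant with thymus collected for manufacture in the denominator, including those later replaced.
- List failures by reason: expansion, release, or below the planned dose. A batch that never reaches formulation is a failure and needs no dose range to be scored.
- Take the planned range as it stood before any reduction under section 8.5; otherwise a short batch would count as meeting its own reduced target. This scores the batch only and does not affect what a child receives.
- Count a released product within range as a success even if it is never infused.
- Keep the amount, total and per kg, as a supporting measure, with 0 where there is no releasable product.

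The cost is a change of wording, since batch records and weights are already held. The downside is that reported feasibility may be less favourable, and at 9 to 12 patients the interval will be wide.
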